## Safety:

Safety will be assessed throughout the study. Baseline and follow-up safety assessments will include height, body mass index (BMI), weight, temperature, medical, visual and ocular history, physical examinations, ocular examinations, visual acuity, color vision tests, electrocardiograms (ECGs), vital signs (VS), clinical laboratory tests (hematology, serum chemistry, and urinalysis), the Profile of Mood States (POMS), the Columbia-Suicide Severity Rating Scale (C-SSRS), the Clinician Administered Dissociative States Scale (CADSS), and adverse events (AEs). Safety assessments will include AEs, ECGs, VS, clinical laboratory results, and physical observations. Assessment of each Subject's level of alertness/Sedation will be accomplished using the Modified Observer's Assessment of Alertness/Sedation (MOAA/S).

Evaluation of safety in the MAD study will utilize the same safety assessments used in the SAD study.

Evaluation of safety in the CSF capture study will utilize the same safety assessments used in the SAD and MAD study with the exception of the CADSS and MOAA/S assessments.

Monitoring of AEs will be governed by change from baselines established during prescreening and Day -1 examinations and clinical laboratory tests. AEs will be coded using the Medical Dictionary for Regulatory Activities (MedDRA) and summarized by system organ class and preferred term, by severity, by relationship to study drug and study procedure, and by study drug dose.

Dose escalation in the SAD study or continued dosing in the MAD study may be stopped according to the predefined halting rules or if a Subject's scores demonstrate acute suicidality on the C-SSRS assessment or at the discretion of the study Principal Investigator and/or sponsor.

Determination of whether to escalate to the next dose level in the SAD study or continue dosing in the MAD will be made by the Principal Investigator in consultation with the Medical Monitor and Study Sponsor.

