## 4.0 STUDY RISKS AND BENEFITS

As with all clinical studies, there are risks. These risks include multiple venipuncture and blood sample collections. The blood sample collection scheme was designed to collect the minimum number of blood samples to collect the needed samples for thorough clinical laboratory testing and that accurately and completely describe the PK of study drug. This minimizes the number of venipunctures and the total volume of blood collected from each Subject during the study. The amount of blood to be collected from each subject over the course of the study is acceptable based on the American Red Cross standard (http://www.redcrossblood.org/donating-blood/eligibility-requirements).

Subjects in the CSF Capture Study will also undergo lumbar puncture with placement of CSF catheter, a procedure associated with risk of bleeding, infection and post-procedure headache. The volume of CSF to be collected at each time point was calculated to be less than the hourly CSF production to minimize risk of headache and subjects will be kept in a semi-recumbent position while the CSF catheter remains in place. Procedures will be performed utilizing standard aseptic technique to minimize infection risk.

Subjects will be asked to provide protected health information (PHI). All attempts will be made to keep PHI confidential within the limits of the law; however, there is a chance that unauthorized persons will see the subjects' PHI. All study records will be kept in a locked file cabinet or maintained in a locked room at the Duke Early Phase Research Unit (DEPRU). Electronic files will be maintained on secure servers and transferred files with PHI will be password protected. Only people involved in the conduct, oversight, monitoring, or auditing of this study will be allowed access to the PHI that is collected. Any publications from this study will not use information that will identify subjects by name. Organizations that may inspect and/or copy research records maintained at DEPRU for quality assurance and data analysis include the local Institutional Review Board (IRB), National Institute of Mental Health and/or their designees, and the FDA.

A description of this clinical study will be available at http://www.ClinicalTrials.gov, as required by US law. This website will not include information that can identify subjects and at most, it will include a summary of the results.

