
 
Activated partial thromboplastin time
 
Prothrombin time
 
International normalized ratio
 
	
 
Cannabinoids
 
Amphetamines
 
Barbiturates
 
Cocaine
 
Opiates
 
Benzodiazepines
 
Phencyclidine
 
Methadone
 
Cotinine
 
Alcohol (Breathalyzer)
 
	
 
Hepatitis B surface antigen
 
Hepatitis C antibody
 
Human immunodeficiency virus 1 & 2 antibodies
 

Table 8: Clinical laboratory evaluations

VS will be monitored according to the Time and Events Schedule for the SAD study (Table 1), MAD study (Table 2), and CSF Capture Study (Table 3) and will include blood pressure, pulse rate, respiration, and temperature. The PI or designee will verify the eligibility of each Subject with out-of-range VS and document approval prior to dosing.

Systemic blood pressure and pulse will be continuously monitored throughout drug administration and for 2 hours after the conclusion of study drug infusion. Monitoring of these parameters will be accomplished with a correct-sized finger cuff placed on either the index or middle finger and the Nexfin noninvasive continuous blood pressure monitor.

The ECG measurements, collected in triplicate, will be monitored using a 12-lead ECG signal according to the Time and Events Schedule for the SAD study (Table 1), MAD study (Table 2) and CSF Capture study (Table 3). During the collection of the baseline ECGs, Subjects should be in a quiet setting without distractions (eg, television or cell phones). Subjects should rest in a recumbent position for at least 5 minutes before ECG collection and should refrain from talking or moving arms or legs. Baseline ECG recordings should be taken at a time independent of blood sampling or VS measurements.

Subjects will be instructed to tell the study physician and/or research personnel of any AEs that occur at any time during the study. Subjects will be monitored for AEs from dose administration through the end-of-study.

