## **12.9 ADVERSE EVENTS MONITORING AND REPORTING**

Subjects will be monitored for any AEs from study drug administration until the end-ofstudy. These will include a full assessment of abuse-related AEs. The Investigator or designee will review each event. The Investigator or designee will assess its relationship to the study drug. Each sign or symptom will be graded for severity and the date and time of onset, cessation, and resolution will be recorded. Treatment of any adverse reactions will be evaluated and managed by the PI, a designated physician or appropriate emergency responders, as appropriate. All nonserious AEs will be reported on a regular basis, or as specified by the Sponsor.

An AE is defined as any untoward medical occurrence associated with the use of a drug in humans, whether or not considered drug related. An AE can be any unfavorable or unintended sign, symptom, or disease temporally associated with the use of a drug, without judgement to causality. An AE can arise from any use of the drug and from any route of administration, formulation, or dose, including an overdose.

A life-threatening AE/life-threatening suspected adverse reaction, in the view of either the Investigator or Sponsor, places the Subject at immediate risk of death. It does not include an adverse reaction that, if it had occurred in a more severe form, may have caused death.

A serious adverse event (SAE) or serious suspected adverse reaction in the view of either the Sponsor or the PI, results in any of the following outcomes.

- 1. Death. The death was the outcome of the AE. Date will be included, if known.
- 2. Life-threatening AE. The Subject was at substantial risk of dying at the time of the AE, or continued use of the Clinical Trial Material may have resulted in the death of the patient.
- 3. Inpatient hospitalization or prolongation of existing hospitalization. Emergency room visits that don't result in admission to the hospital should be evaluated for other serious outcomes.
- 4. Disability or permanent damage. A substantial disruption in a person's ability to conduct normal life function. For example, the AE resulted in a significant, persistent, or permanent change, impairment, damage, or disruption in the patient's body function, body structure, physical activities, and/or quality of life.

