### Table 11: Blood draw volumes and uses for CSF Capture study

Sample	Total Volume (mL)	Clin. Lab. Volume	PK Volume (mL)
_		(mL)	
Screening Draw	20	20	NA
Day -1 Draw	11	11	NA
Day 1 Draw	16	11	5
(preinfusion)			
Day 1 Draw (end-of-	5	NA	5
infusion)			
Day 1 Draw (1-hour	5	NA	5
after the start of the			
infusion)			
Day 1 Draw (2-hour	5	NA	5
after the start of the			
infusion)			
Day 1 Draw (4-hour	5	NA	5
after the start of the			
infusion)			
Day 1 Draw (8-hour	5	NA	5
after the start of the			
infusion)			
Day 1 Draw (12-hour	5	NA	5
after the start of the			
infusion)			
Day 2 Draw (24-hour	16	11	5
after the start of the			
infusion)			
Total Blood Draw	93		

Sample	Total Volume (mL)	Proteomics Volume (mL)	Metabolomics Volume (mL)	PK Volume (mL)
Day 1 Draw (preinfusion)	10	3.5	3.5	3
Day 1 Draw (end-of- infusion)	10	3.5	3.5	3
Day 1 Draw (8-hour after the start of the infusion)	10	3.5	3.5	3
Total CSF Draw	30	10.5	10.5	9

Table 12: CSF draw volumes and uses for CSF Capture study

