6.2 Safety Population

All participants who received at least one dose of study medication. This includes any subjects who were replaced and received at least one dose.

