12.6 Adverse Events

An adverse event (AE) is any untoward medical occurrence in humans, whether or not considered drug-related, which occurs during the conduct of a clinical trial. (Any change in clinical status, routine labs, x-rays, physical examinations, etc.), that is considered clinically significant by the study investigator is considered an AE. All AEs will be coded using the Medical Dictionary for Regulatory Activities (MedDRA) central coding dictionary.

Adverse reaction is any adverse event caused by the drug. Suspected adverse reaction is any adverse event for which there is a reasonable possibility that the drug caused the adverse event. A reasonable possibility implies that there is evidence that the drug caused the event. An event will be considered Related to study drug if the investigator deems the event relationship as Possible, Probably, or Definite. An event is Not Related if the investigator classified the event relationship to study drug as Unlikely or Not Related. Expectedness and Severity (Mild, Moderate, Severe) of event will also be collected.

An AE or Suspected Adverse Reaction (SAR) or Adverse Reaction is considered "Serious" if, in the view of either the investigator or sponsor, it results in any of the following outcomes:

- Results in death
- Is life-threatening (places the subject at immediate risk of death from the event as it occurred)
- Results in inpatient hospitalization or prolongation of existing hospitalization
- Results in a persistent or significant disability or incapacity
- Results in a congenital anomaly or birth defect
- An important medical event that may not result in death, be life threatening, or require hospitalization may be considered a serious adverse event (SAE) when, based upon appropriate medical judgment, the event may jeopardize the subject and may require medical or surgical intervention to prevent one of the outcomes listed in this definition.

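### In the CSF part the stated adverse event window opens at dosing, after the implied lumbar puncture; the AE start, procedure relatedness and reporting of undosed subjects need reconciling

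*Protocol*

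**What the plan says.** **AE window.** Protocol 12.9: "Subjects will be monitored for any AEs from study drug administration". Protocol 12.8: "Subjects will be monitored for AEs from dose administration through the end-of-study". The AE definition in 12.9 is tied to use of a drug.

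**Procedure.** Protocol 4.0: "Subjects in the CSF Capture Study will also undergo lumbar puncture with placement of CSF catheter, a procedure associated with risk of bleeding, infection" and headache. The Synopsis (Pharmacokinetics), 8.6, 12.11 and Table 12 all place the first CSF sample before the infusion. Section 12.11 says samples come through a spinal catheter and leaves placement details to the Manual of Procedures (MOP).

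**After an AE.** Protocol 12.9 requires sensory and motor/neurological testing, vital signs and a Day 30 phone call, and allows extra blood or CSF samples.

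**Analysis.** The Safety Population in SAP 6.2 is "All participants who received at least one dose of study medication". SAP 12 makes it the default for all analyses and SAP 12.5 for safety analyses. Protocol 10.2 replaces subjects who withdraw before dosing.

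**Relatedness.** The Synopsis (Safety) promises AEs "summarized by system organ class and preferred term, by severity, by relationship to study drug and study procedure, and by study drug dose"; sections 8.7 and 13.1 repeat this. Protocol 12.9 and SAP 12.6 define relatedness to the product only.

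**Wider text.** SAP 12.6 defines an AE as an occurrence "which occurs during the conduct of a clinical trial", with no dosing start.

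**The concern.** In the SAD and MAD parts the scheduled pre-dose procedures are minor, so a window that opens at dosing loses little. In the CSF part the main foreseeable procedural risk begins before the infusion. Site staff who follow 12.8 and 12.9 literally could leave a painful or failed placement, a faint, or minor bleeding off the AE record if it settled before dosing. The neurological checks and Day 30 call depend on there being an AE, so they would not be prompted either.

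Two analysis problems follow. A subject harmed by the procedure and then not dosed is missing from the AE tables. And a procedural event that is recorded has no defined rating for relationship to the procedure, so a post-puncture headache may be judged only against the drug. These are healthy volunteers with no therapeutic benefit, so an accurate account of procedure harm matters even in a small cohort.

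**Working it through.** No sample-size or power formula is involved. The check is whether the provisions fit together.

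**1. Does access precede dosing?** Table 12 lists three CSF draws, the first preinfusion. Its figures reproduce: 3.5 + 3.5 + 3 = 10 mL per draw, and 3 × 10 = 30 mL in total. The text of 12.11 can be read as about 10 mL in total per subject, so the preinfusion volume is uncertain, but the timing is not. A preinfusion sample through a catheter placed for sampling requires access before dosing. This is an inference, because the MOP was not available.

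**2. Which events fall outside the stated window?**

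| Event | Position under the documents |
|---|---|
| Serious, before infusion | SAE reporting (12.9) and the study halting rule (10.3) state no dosing start, so it appears covered |
| Non-serious, persisting into the infusion | Present once the window is open, so it is recorded and triggers the checks |
| Non-serious, resolved before infusion | Outside the window in 12.8 and 12.9; inside the wider wording of SAP 12.6 |

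The gap is the third row.

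**3. What happens to a catheterised, undosed subject?** The subject is replaced (10.2), is outside the Safety Population (SAP 6.2), and so is outside the AE summaries (SAP 12, 12.5). If already randomized, the subject appears in the disposition table with a reason for discontinuation (SAP 12.1). As an illustration only, suppose the cohort is filled by replacement and one undosed subject had the only procedural event:

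- 8 dosed: the Safety Population shows 0/8; all catheterised subjects would show 1/(8 + 1) = 1/9 = 11.1%.
- 6 dosed: 0/6 against 1/(6 + 1) = 1/7 = 14.3%.

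Both sizes are shown because protocol 7.0 and 12.4 and SAP 10 plan 8 CSF subjects while the protocol Synopsis plans 6. The documents give no rate of procedural events or of failure to dose after catheterisation, so no expected count is offered.

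**4. Can the promised procedure-relatedness summary be produced?** Protocol 12.9 has the investigator assess relationship to study drug and defines Related and Not Related by reference to the product. SAP 12.6 groups its categories by relationship to study drug. The output is promised, but its input is undefined.

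**5. Can pre-dose and post-dose events be told apart?** SAP 7 sets a missing AE start day to the day of study drug administration and treats the event as treatment emergent. A procedural event with a missing start day would then count as treatment emergent. The SAP describes no pre-dose flag.

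**The case against.** The strongest reply is that the documents, read together, already intend wider capture. In 12.8, the sentence just before the monitoring start tells subjects to report AEs arising at any time in the study. Table 3 ticks adverse events for Day 1 as a whole. The Synopsis and 8.7 judge AEs against prescreening and Day -1 baselines. Section 13.1 requires procedure-related AEs to be listed, and 12.9 has all AEs entered on the case report form. SAE reporting applies whatever the relationship to the product. Undosed subjects do not vanish either: the Table 3 footnote gives withdrawing subjects an early termination visit. Neurological function is part of the physical examinations on Days 2 and 3.

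All of this stands, and it limits the point. A reader might infer that the plan would record none of the pre-dose procedural harms. The documents do not support that, because volunteered reports, the Day 1 tick and the SAE rules leave routes for capture. Nor do they support any expected number of missed events, since any rate would be assumed.

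The reply does not remove the conflict. The only explicit statements of when monitoring starts, in 12.8 and 12.9, both say dosing, and no passage sets an earlier start for the CSF part. Listing procedure-related AEs does not say when their collection begins. Staff could follow either reading in good faith and record different things.

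**Conclusion.** The point holds as a conflict between provisions. The stated AE start falls after the implied start of the lumbar procedure. Non-serious procedural events that resolve before the infusion therefore need not be recorded as AEs or trigger the post-AE checks. Catheterised subjects who are never dosed are left out of all AE summaries and appear at most in Randomized Population disposition. Procedure relatedness is promised but not defined.

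The scope is the CSF cohort: every subject in it is exposed to the gap, but only one class of event and any undosed subjects are affected. The frequency cannot be estimated from the documents. The conclusion rests on inferring placement before infusion from the preinfusion sample, and on the MOP not already setting an earlier AE start. It does not depend on the CSF volume or on whether 6 or 8 subjects are enrolled. The amendment is worth making because it improves the procedural safety record at little cost.

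**What to change.** For the CSF part:

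1. Amend protocol 12.8 and 12.9 so that AE collection opens at the start of lumbar puncture/catheter placement, or at Day -1 check-in. This brings them into line with 13.1 and SAP 12.6.
2. Flag events before the infusion as pre-dose, not treatment emergent, and state how the SAP 7 missing-date rule applies to them.
3. Record relationship to the lumbar procedure in its own field, with a definition, beside relationship to study drug.
4. In the SAP, list pre-dose procedural events for all subjects in whom placement was attempted, including those never dosed. A separate analysis population is optional at this cohort size.

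The cost is a few sentences in each document, one case report form field, one listing and a few more AE records. Dosing and treatment are unchanged.

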### **Duration of patient participation in study:**

Participants in the SAD study: each Subject will participate in one treatment period. A treatment period consists of residential stay on days -1 to 2 inclusive with 1 follow up visit (Day 3) and phone call (Day 5-8).

Participants in the MAD study: each Subject will participate in one treatment period. A treatment period consists of residential stay on days -1 to 5, with discharge the morning of day 5 and re-admission on day 712 inclusive with 1 follow up phone call (Day 15) and phone call (Day 17-19).

Participants in the CSF capture study: each Subject will participate in one treatment period. A treatment period consists of residential stay on days -1 to 2 inclusive with 1 follow up visit (Day 3) and phone call (Day 5-8).

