#### Study Halting Rules

If any of the following events occur, the study will be stopped:

- Any subject develops an SAE through the last study visit.
- 2 or more subjects in any cohort experience a Grade 3 (severe) AE, including unsolicited clinical, ECG, VS, and laboratory AEs, that is of the same type (preferred term) and occurring in the same SOC.
- Any subject develops an episode of anaphylaxis within 24 hours after receiving the study drug.

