#### Dose Escalation Halting Rules

The PI must review the following criteria before dose escalation:

- SAD: A review of all available safety data for the cohort to Day 3 demonstrates that the study halting criteria described below have not been met.
- MAD: A review of all available safety data to Day 12, at a minimum, demonstrates that the dose-escalation halting criteria described below have not been met.

If any of the following dose escalation halting rules are met in either the SAD or MAD parts, escalation to the next planned dose cohort will not proceed until all available study data have been reviewed by the PI, the Medical Monitor and the Study Sponsor:

- Any subject develops an SAE.
- Any subject experiences a Grade 3 (severe) AE.
- 2 or more subjects in a cohort experience a Grade 2 (moderate) or greater AE that is of the same type (preferred term) and occurring in the same SOC.

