An unexpected AE is defined as an AE or suspected adverse reaction that is not listed on the PI's Brochure or is not listed at the severity indicated. If the IB is not available, an unexpected AE is one that is not consistent with the risk information described in the general investigational plan or elsewhere in the current application, as amended.

The PI or designee will notify the appropriate sponsor contact immediately after SAE detection, observation, or report of occurrence, regardless of relationship to test article.

Serious AE reports should contain the following details.

- A. Study name/number.
- B. Study Drug.
- C. Investigator details (name, phone, e-mail).
- D. Subject numbers.

- E. Subject initials.
- F. Subject Demographics.
- G. Clinical Event.
  - a. Description.
  - b. Date of Onset.
  - c. Treatment (Drug, dose, form).
  - d. AE relationship to study drug.
  - e. Action taken regarding study drug in direct relationship to the AE.
- H. If the AE was fatal or life threatening.
- I. If applicable, cause of death (including whether or not the death is related to study drug).
- J. If applicable, autopsy findings (if available).

In the event of an AE or SAE, the following safety measurements will be performed and recorded.

- A. Sensory test (pinprick and vibration)
- B. Motor examination, reflexes and assessment of coordination (neurological exam)
- C. Vital signs
- D. Additional blood and/or CSF samples may be obtained, at the discretion of the investigator.
- E. Day 30 (+/- 3 days) phone follow up.

Any new SAE that occurs within one month after the last dosing in the study and is considered to be related to the investigational product should be recorded and reported immediately to the Sponsor. The person responsible for this study shall take care that this study has been carried out in accordance with pharmacovigilance local regulations.

All serious AE reporting will adhere to the U.S. Code of Federal Regulations (21 CFR Part 312.32) for IND drugs (15-Day alerts). The IRB will be notified of the alert reports per FDA regulations. All AEs including SAEs will be followed to resolution when possible. All AEs and treatment administered will be recorded on the case report form. The sponsor will be responsible for reporting and processing any SAEs to the FDA or other applicable regulatory agency.

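### The one-month window for related SAEs runs 22 to 26 days past the last scheduled contact, and the only later call depends on an earlier AE

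*Protocol*

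**What the plan says.** **Reporting window.** Protocol section 12.9 applies to "Any new SAE that occurs within one month after the last dosing in the study and is considered to be related" to the investigational product. Such events are to be recorded and reported to the sponsor at once.

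**Scheduled contact.** The synopsis (duration of participation) ends SAD and CSF follow-up as "inclusive with 1 follow up visit (Day 3) and phone call (Day 5-8") and MAD follow-up as "follow up phone call (Day 15) and phone call (Day 17-19"). The adverse-event and phone-call rows of protocol Tables 1-3 and of SAP sections 3.1-3.3 stop on the same days. Section 12.16 requires subjects to attend what those tables list. Section 12.8 tells subjects to report AEs that occur during the study, and section 12.9 monitors AEs until end of study.

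**Later contact.** Section 12.9 opens a list with "In the event of an AE or SAE, the following safety measurements will be performed and recorded". Its last item is "Day 30 (+/- 3 days) phone follow up". The call appears in no schedule table and nowhere in the SAP.

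**Related rules.** The study halting rule in section 10.3 counts "Any subject develops an SAE through the last study visit". The escalation halting rule says "Any subject develops an SAE", with no time limit. Elsewhere section 12.9 requires SAEs to be notified to the sponsor whatever their judged relationship to treatment.

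**The concern.** The protocol sets a one-month window for late related SAEs but schedules no contact that would observe most of it. The one contact that comes close goes to subjects who have already had an AE. A subject with a mild early AE is asked again around Day 30. A subject without one has no scheduled contact after the Day 5-8 or Day 17-19 call.

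This is a first-in-human study with safety as a primary objective, and AEs are to be summarised by dose and against pooled placebo. If early AEs are more frequent on active drug or at higher doses, late questioning will be more frequent there too. The completeness of late safety data would then differ between the groups being described.

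**Working it through.** The plan gives no coverage figure to reproduce, so the check is day arithmetic. One month is taken as 30 days, an assumption that is varied below.

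**Inputs**
- Last dose: Day 1 in SAD (Table 1) and CSF (section 7.0); Day 11 in MAD (section 6.0).
- Last scheduled contact: Day 5-8 in SAD/CSF; Day 17-19 in MAD.
- Conditional call: Day 30 ± 3, that is Day 27-33.

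**Formulas.** Reach of scheduled contact = last contact day − last dosing day. Gap = 30 − reach. Share covered = reach / 30.

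| | SAD/CSF | MAD |
|---|---|---|
| Window ends | 1 + 30 = Day 31 | 11 + 30 = Day 41 |
| Reach | 5−1 = 4 to 8−1 = 7 days | 17−11 = 6 to 19−11 = 8 days |
| Gap | 30−7 = 23 to 30−4 = 26 days | 30−8 = 22 to 30−6 = 24 days |
| Share covered | 4/30 = 13% to 7/30 = 23% | 6/30 = 20% to 8/30 = 27% |

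With a month of 28 to 31 days, the gap is 21-27 days in SAD/CSF and 20-25 days in MAD.

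**Conditional call, if Day 30 is a study day**
- SAD/CSF: 27−1 = 26 to 33−1 = 32 days after the dose, so close to or past the end of the window.
- MAD: 27−11 = 16 to 33−11 = 22 days after the fourth dose. This leaves 30−22 = 8 to 30−16 = 14 days uncovered, even for subjects who get the call.

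The text does not say whether Day 30 counts from study start, from the last dose or from the event. The MAD figures hold only for the first reading.

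**Check against stated durations (section 12.4).** About 33 days for SAD and CSF equals 28 screening days + 5, the early end of the call window; the late end gives 28 + 8 = 36. About 52 days for MAD exceeds 28 + 19 = 47. A routine Day 30 call would need 28 + 30 = 58. Neither figure leaves room for it.

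**Dependence on arm or dose.** In any group, the share given the late call equals the share with an AE. Groups differ in late questioning only to the extent that their AE incidence differs; with equal incidence there is no difference. The documents give no expected AE incidence, so no size can be attached.

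**The case against.** **A reporting duty is not a promise of active follow-up.** The one-month sentence can be read as governing events the site happens to learn of. This stands: a reader might infer that section 12.9 contradicts Tables 1-3, but nothing in the documents commits the site to active contact for a month. The gap is in what can be observed.

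**The Day 30 call is event follow-up.** It sits beside a sensory test, a neurological examination and vital signs, and the revision history logs the addition as AE response procedures. That is the natural reading of its purpose. It is still the only contact after the routine schedule. If it was meant for the CSF part alone, which the text does not say, the 48 + 16 = 64 SAD and MAD subjects have no late contact.

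**Late events may surface anyway.** Subjects can volunteer them, and serious events are the least likely to depend on a call. Section 12.3 mentions a subject register for long-term follow-up if needed, and the consent pages, which could carry reporting instructions, are not available here. This stands, so the point is limited to scheduled contact and active questioning.

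**Bias between arms.** A reader might divide an assumed AE rate on active by one on placebo and call the result a detection ratio. That only returns the assumption, and it supposes that nothing is found outside the call. The SAP plans descriptive safety summaries without hypothesis tests, specifies no comparison of late events, and the placebo groups are small (12 in SAD, 4 in MAD, 2 or 3 in CSF depending on the section).

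**Halting.** A reader might infer that an SAE after a subject's last visit escapes the halting rules while a higher cohort is being dosed, since SAD escalation review needs data only to Day 3. The documents do not support that. The escalation rule has no time limit, section 8.7 lets escalation or continued MAD dosing stop for any further reason, and section 14.6 defines study completion by the last subject's last visit. Read at study level, a late SAE from an early cohort can meet the halting rule. What remains is an ambiguous term.

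**Related-only wording.** It may be an added duty after study exit, on top of the general rule. That is reconcilable, but the protocol does not say where one rule ends and the other begins.

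**Conclusion.** The point holds as a limited but worthwhile improvement. For a subject without an AE, 23-26 of 30 post-dose days in SAD/CSF and 22-24 of 30 in MAD have no scheduled contact. Later active questioning depends on having had an AE. These figures rest on the schedule days and a 30-day month; 28 or 31 days changes them little. The shortfall of the Day 30 call in MAD also assumes that it means study day.

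The effect is on the completeness and evenness of late safety data. No sample size, power or error rate is affected. The size of any difference between arms or doses cannot be given from the documents.

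**What to change.** - Make one late AE/SAE phone contact unconditional for every dosed subject, timed about one month after that subject's last dose. With a 30-day month that is about Day 31 in SAD/CSF and Day 41 in MAD. Add it to protocol Tables 1-3 and SAP section 3.
- State the starting point from which the existing Day 30 call is counted.
- Reconcile the related-only wording of the one-month sentence with the requirement, in the same section, to report SAEs whatever their judged relationship.
- State whether the last study visit in the study halting rule is the subject's or the study's.

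The choice of halting rule and of AE-triggered examinations stays with the sponsor.

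**Cost.** At most 48 + 16 + 8 = 72 short calls (70 if the synopsis count of 6 CSF subjects applies), fewer where the call would be made anyway, plus wording changes in both documents. Last-subject-out moves by about three weeks. No new type of procedure is needed, because the protocol already plans this call for some subjects.
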